1 ETHICS/PROTECTION OF HUMAN SUBJECTS

1.1 Institutional Review Board (IRB)

This study will be conducted in compliance with current Good Clinical Practices (GCP) and Title 21 Part 56 of the United States of America Code of Federal Regulations (CFR) relating to IRBs.

1.2 Ethical Conduct of Study

The study will be conducted in accordance with GCP defined by the International Conference on Harmonisation (ICH) and the ethical principles of the Declaration of Helsinki.

1.3 Subject Information and Consent

This study will be conducted in compliance with Title 21 Part 50 of the United States of America Code of Federal Regulations (CFR), Federal Regulations, and ICH Guidance Documents pertaining to informed consent. At the first visit, prior to initiation of any study-related procedures, subjects will be informed about the nature and purpose of the study, participation/termination conditions, and risks and benefits. Subjects will be given adequate time to ask questions and become familiar with the study prior to providing consent to participate. Subjects will give their written consent to participate in the study and will be provided with a copy of the fully executed consent form for their records.

2 INTRODUCTION: BACKGROUND INFORMATION AND SCIENTIFIC RATIONALE

2.1 Background Information

2.1.1 Alzheimer's Disease and Mild Cognitive Impairment

Alzheimer's disease (AD) is the most prevalent form of dementia affecting more than 5,000,000 people in the US and an estimated 20,000,000 people worldwide, according to the Alzheimer's Association¹. AD causes progressive neuronal degeneration, resulting in progressive memory loss, dementia and death. AD has no known cure or preventative as yet; however, treatments exist that can temporarily and modestly at best ameliorate dementia symptoms.

Mild cognitive impairment (MCI) is the term used when there is clinical concern about cognitive decline and evidence of impairment(s) in cognitive testing, more than expected for the patient's age and educational background, but not so severe that the person cannot manage their daily functioning without more than minimal assistance. MCI is frequently, though not always, a transitional, prodromal phase of dementia due to Alzheimer's disease. "Dementia" is present when independent daily functioning is affected.

AD is characterized by the presence of amyloid- β (A β) plaques, tau neurofibrillary tangles and loss of neurons and synapses in the cerebral cortex, particularly in association areas that subserve cognition. A β has been the target of many recent clinical trials; however, these studies have failed to find that reducing amyloid meaningfully slows progression of dementia. It is increasingly evident that AD is a complex disorder with multiple metabolic, inflammatory, vascular and other pathophysiological processes beyond amyloid and tau proteinopathies contributing to neurodegeneration. There is now increasing attention to intervening in these non-amyloid pathways to stem the tide of neurodegeneration in AD.

2.1.2 Alzheimer's Disease and the Immune Response

Inflammation and immune responses (IIR) have major roles in the pathophysiology of Alzheimer's disease (AD). IIR encompasses many complex and highly regulated biological processes with which immune local tissue cells respond to tissue injury and maintain organ function and organismal homeostasis. AD's pathognomonic amyloid- β (A β) peptide itself is hypothesized to be a dysregulated ancient innate immune response to allo- or auto- stimuli in the brain.² A β oligomers and aggregates in AD are thought to elicit or exacerbate IIR,³ promoting vicious cycles of protein misfolding, endoplasmic reticulum stress, deranged metabolic signaling and mitochondrial function, oxidative/nitrosative stress, and cell death. There is tremendous interest and rapidly growing academic, biotech and pharma research on IIR therapeutic approaches in AD and AD-related disorders as similar vicious cycles have been proposed for a-synuclein pathologies in LBDs,^{4,5} tau pathologies in FTD-tau and other tauopathies,^{6,7} and TDP-43 pathology in FTD-TDP and ALS.^{8,9}

Peripheral inflammatory markers may serve as biomarkers of AD disease state and distinguish healthy older adults from middle-aged adults, and healthy older adults from those with mild cognitive impairment (MCI) or Alzheimer's Disease¹⁰. Inflammatory biomarkers may even predict those who will convert from MCI to AD over a two-year period¹¹⁻¹³. Innate immune function is affected by progression of AD; Monocytes of subjects with MCI or AD induce a greater NLRP3 and NLRP1 inflammasome response to extrinsically applied amyloid beta than do healthy controls¹⁴. The adaptive immune system is also involved in AD progression: T-cell reactivity to amyloid beta increases with age as well as progression of AD¹⁰, and with worsening disease, clonal populations of CD4+ and CD8+ T-cells can be found in the cerebrospinal fluid^{15,16}. Regulatory T cells (Tregs) are of particular significance to AD. While augmenting Tregs increases the number and function of microglia

associated with amyloid beta plaques, and improves cognitive functions^{12,17-19}, they are fewer in number over the course of disease²⁰.

There is tremendous and rapidly growing academic, biotech and pharma research on IIR therapeutic approaches in AD and AD-related disorders as similar vicious cycles have been proposed for α -synuclein pathologies in LBDs,^{5,21} tau pathologies in FTD-tau and other tauopathies,^{22,23} and TDP-43 pathology in FTD-TDP and ALS.^{24,25}

2.1.3 BCG Rationale

A potentially transformative IIR approach to AD prevention and disease modification that is safe, cheap and ready for testing *now* is *Bacillus Calmette-Guérin* (BCG) vaccination. Live BCG vaccination has been the mainstay of prevention of tuberculosis for almost 100 years, administered in billions of people in more than 180 countries, from infants to the elderly. Its only significant contraindication is immunocompromise. "Off-target" benefits of BCG vaccination were recognized early in its 40% reduction of all-cause mortality in children and its prevention of non-mycobacterial infections,^{26,27} and BCG is now being explored in clinical trials as a prophylaxis against COVID-19.²⁸ BCG has also demonstrated utility in treating non-infectious diseases. One major use is as a treatment for non-muscle-invasive bladder cancer, where high-dose intravesicular infusion is a treatment of choice,²⁹ and there has been interest in BCG's beneficial associations and effects in other cancers,³⁰⁻³² multiple sclerosis³³⁻³⁵ and type 1^{36,37} and type 2 diabetes.³⁸⁻⁴¹

In the CNS, 'sterile inflammation' resulting from autoimmunity, misfolded proteins, or cell damage or death can result in a neurotoxic environment if not adequately kept in balance. T-regulatory cells, or Tregs can regulate immunologic balance by controlling microglial and antigen presenting cell (APC) activation, inhibiting effector T (Teff) cells, and inducing astrocytic release of neurotrophins, thus effectively transforming a neurotoxic environment to a neurotrophic state. For example, two studies noted decreased neuronal cell death in a MPTP model of Parkinson's Disease, finding that the magnitude of dopaminergic preservation correlated with the magnitude of Treg response to BCG treatment.^{42,43} BCG's ability to induce and/or restore Treg immune balance is of great interest for treatment in AD,^{44,45} where preclinical models find that augmenting Tregs increases the number and function of microglia associated with plaques, and improves cognitive functions.^{18,46,47} In AD, Tregs may be overwhelmed due to their low numbers or dysfunction;⁴⁸ BCG may increase Treg number and function to rebalance the neurotoxic state to one of neuroprotection.⁵

Limited but provocative epidemiological analyses and *in silico* trial data support a benefit of BCG for AD. A large retrospective analysis found that older, non-demented adults treated with intravesicular BCG for bladder cancer had a significant 4-fold lower risk of subsequent AD over a median 8-year follow-up period than those treated with other means.⁴⁵

BCG, a highly safe, live, attenuated vaccine used throughout the world to prevent tuberculosis and confers many health-promoting non-specific effects, from preventing infectious disease to treating cancers. These effects rely on its induction of trained and heterologous immune responses in the host. Such immune effects directly overlap and influence immune responses known to occur in CNS disease; non-human studies have found benefit to BCG vaccination on models of Parkinson's and Alzheimer's diseases, including cognitive improvement. These studies provide the impetus for our initiating clinical trials with BCG oriented towards primary prevention of AD in older adults or disease modification and secondary or tertiary prevention in adults whom AD pathological changes are already in motion. This pilot study initiates this program, with focus on the immune consequences of treatment and potential changes in AD-specific biomarkers and cognition after vaccination.

3 STUDY DESIGN

3.1 Overall Study Design and Plan

This single-site, open-label clinical trial will investigate the immune and neurobiological biomarker effects of BCG vaccination in healthy older adults and older adults with mild cognitive impairment (MCI), and gather data on tolerability, safety and study feasibility. Twenty participants (approx. n=10 cognitively normal, n=10 mild cognitive impairment) will receive two intradermal BCG vaccinations spaced 4 weeks apart and will be evaluated 12 weeks after the initial immunization. Cerebrospinal fluid (CSF) and blood will be collected at Screening (blood only), Baseline, Week 4 (blood only), and Week 12 for to assess safety, IIR and AD biomarkers.

3.2 Study Objectives

The primary objective of this study is:

1. To determine the most promising biomarkers of IIR and neurodegeneration in blood and CSF in terms of feasibility of measurement, technical specifications, and BCG response of assays.

The secondary objectives of the study will be:

1. To evaluate clinical neurobehavior changes from Baseline, including (MoCA, RBANS, NPI-Q and FAQ) following BCG vaccination.
2. To assess the safety and tolerability of BCG vaccination in healthy older adults and older adults with MCI.

3.3 Study Outcome Measures

3.3.1 **CSF and Blood Biomarker Outcomes**

CSF and blood will be collected at Baseline, Day 28 (blood only) and Day 84 Visits to examine biochemical biomarkers of:

1. Target engagement: BCG, purified protein derivative (PPD) and / or mycobacterium tuberculosis (heat-killed, mTB) – induced cytokine response in peripheral blood cells will be used to evaluate for BCG vaccine-induced immunity.
2. Pharmacodynamic response: a) Circulating cytokines and other related blood- and CSF-based IIR biomarkers relating to innate and adaptive immune responses; b) Epigenetic changes in peripheral blood cells and / or CSF- derived cell populations as indicators that BCG can lead to long term changes in peripheral and central nervous system immune cells.
3. AD pathophysiology: Amyloid- β 42/40, phospho-tau, total tau and / or neurofilament light protein biomarkers (ATN) and other exploratory AD-relevant synaptic and IIR biomarkers may be compared within subjects over time and between subjects and groups.
4. BCG effects on the interactions of IIR and amyloid: We will perform PBMC stimulation with A β 42 and positive-control antigens (e.g. lipopolysaccharide) and measure the molecular response in the supernatant at multiple timepoints after BCG /treatment. A β 42 has immunostimulatory / inflammatory effects that increase with AD progression and may be modulated by an immune-provoking stimulus such as BCG.
5. Additional related Alzheimer's Disease and immune measures in plasma, CSF, and their cell populations at the transcriptional, protein, or epigenetic levels.

We have several robust platforms in the [name] lab (which serves as the Biomarker Core of the Massachusetts Alzheimer's Disease Research Center) to conduct these assays, including highly validated Euroimmun assays, Fujirebio Lumipulse assays, Meso Scale Discovery with plates run on a new Tecan EV0200 multi-functional robotic liquid handling platform, and Quanterix SR-X for ultrasensitive Simoa assays. We have exhaustively validated many assays specifically for use in short-term clinical trials⁴⁹, and all assays that we propose demonstrate good precision and biotemporal stability. Change in a composite score from Baseline will be used as an outcome of response to BCG.

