4.1.1 Inclusion Criteria

Study subjects meeting all of the following criteria will be allowed to enroll in the study:

1. Individuals between the ages of 55-80;
2. MoCA ≥ 18 ;
3. Normal cognition as defined by MoCA ≥ 26 or MCI as defined by the NIA-AA Workgroup (2011) and MoCA score between 18 and 25 (inclusive);
4. Education level, English language skills and literacy indicates subject will be able to complete all assessments;
5. Ability to provide informed consent;
6. Willing and able to complete all assessment and study procedures, including blood and lumbar punctures, and clinical assessments;
7. If on cholinesterase inhibitor and/or memantine, doses are stable for 3 months prior to baseline;
8. Negative test results for HIV antibody and Tuberculosis (QuantiFERON) at screening;
9. No prior BCG exposure either through birth vaccinations (born in North American) or BCG bladder cancer treatment.
10. Documentation of current flu season vaccination dated at least 14 days prior to baseline visit.

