4.1.2 Exclusion Criteria

Subjects meeting any of the following criteria during the screening evaluation will be excluded:

1. History of chronic infectious disease, such as HIV or untreated or active hepatitis;
2. History of tuberculosis, positive interferon-gamma release assay (IGRA, also known as the QuantiFERON-TB test), including a test with a high reactivity to mycobacteria of non-tuberculosis variety;

3. Prior BCG vaccination, positive T-spot tuberculosis test or a T-spot test showing significant Mycobacteria exposure;
4. A positive SARS-CoV-2 PCR result within 3 months of screening, or known close contact with a confirmed COVID-19 positive person or symptoms highly suspicious for COVID-19 (per CDC guidelines) within 1 month of screening, including fever, cough, shortness of breath, chills, muscle pain, new loss of taste or smell, vomiting or diarrhea, and/or sore throat, based on clinician's judgment;
5. History of treatment with metformin within the past one year;
6. Previous participation (ever) in active immunization research for AD or passive immunotherapy or other disease-modifying treatments for AD within the past three months;
7. Current treatment with immunosuppressants (calcineurin inhibitors, corticosteroids, or biological or cytotoxic immunosuppressants, or disease or condition likely to require high dose steroid or immunosuppressive therapy);
8. Other conditions or treatments associated with increased risk of infections or treatment with immunosuppressive medications for any reason;
9. Current treatment with aspirin > 160 mg/day or chronic, daily NSAIDs;
10. Chronic use of antibiotics;
11. History of keloid formation;
12. Living with someone who is immunosuppressed and/or at high risk for infectious diseases (for example, HIV+ or taking immunosuppressive medications for any reason), or in a job (e.g. healthcare) in which the subject works with immunosuppressed populations;
13. Other/confounding neurological or psychiatric condition, unstable medical or psychiatric conditions, contraindications to BCG use and lab abnormalities or concurrent medication use posing risk for BCG or study procedures;
14. Laboratory abnormalities in B12, Folate, TSH, or other common laboratory parameters that may contribute to cognitive dysfunction;
15. Laboratory abnormalities in CBC, electrolytes, LFTs, BUN, Cr, total serum immunoglobulins, ESR, CRP, or urinalysis posing risk to treatment with BCG per clinician judgment;

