6 STUDY PROCEDURES

6.1 Schedule of Events

Activity	Phone Screen	Screening Visit	Baseline Visit/ BCG Vaccine 1	BCG Vaccine 2	Outcome Visit/ Early Termination	Check-In Phone
		<-28days	Day 1	Day 28 +14 days	Day 84 ±5 days	Day 98 ±5 days
Informed Consent		x				
Inclusion/Exclusion Review	x	x				
Demographics	x	x				
Create IBCID		x				
Medical History	x	x				
Concomitant Medication Review	x	x	x	x	x	x
Family History		x				
Vital Signs, Height, Weight ¹		x	x	x	x	
Physical & Neurological Exam		x				
Screening Lab Tests for Eligibility ²		x				
BCG Vaccination			x	x		
Vaccination Site Monitoring			x	x	x	
Fundoscopy					x	
Safety Lab Tests ³				x	x	
Blood Draw for Biomarkers ⁴			x	x	x	
COVID-19 Testing ⁵		x				
PT/INR		x			x	
Fasting Lumbar Puncture for Biomarkers ⁴			x		x	
MoCA and FAQ		x			x	
Cognitive/Behavioral Assessment ⁶			x		x	
Adverse Event Review		x	x	x	x	x

[1] Height and weight will be measured and recorded at the Screening visit only.

[2] Eligibility lab tests include CBC with diff, CMP, TSH, Folate, B12, HIV antibodies, serum immunoglobulins, ESR, CRP, QuantiFERON-TB Gold Test, urinalysis

[3] Safety lab tests include CBC with diff, CMP, CRP and ESR.

[4] Blood biomarkers will include PBMCs for PPD and amyloid-beta stimulation assay / flow cytometry, and serum for IIR and AD biomarkers. CSF biomarkers will be used for cytology, IIR and AD biomarkers tubes for monocyte levels of innate immunity.

[5] COVID-19 Testing includes SARS-CoV-2 PCR (nasal swab)

[6] Cognitive assessments will include RBANS, NPI-Q

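### BCG response is not summarised by Baseline amyloid status, although the cohorts are defined only clinically and pre-dose CSF is collected, so a response that differs by amyloid status could be averaged away

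*Combined protocol and SAP*

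**What the plan says.** **Cohorts.** Section 3.1 plans about 10 cognitively normal subjects and 10 with MCI. Inclusion criterion 3 in section 4.1.1 assigns them: "Normal cognition as defined by MoCA ≥ 26 or MCI as defined by the NIA-AA Workgroup (2011) and MoCA score between 18 and 25 (inclusive". No inclusion or exclusion criterion names amyloid, tau or another AD marker, and neither does any screening test. The note to the schedule in section 6.1 reads: "Eligibility lab tests include CBC with diff, CMP, TSH, Folate, B12, HIV antibodies, serum immunoglobulins, ESR, CRP, QuantiFERON-TB Gold Test, urinalysis".

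**Link to AD.** Section 2.1.1 states: "MCI is frequently, though not always, a transitional, prodromal phase of dementia due to" Alzheimer's disease. Section 2.1.3 separates primary prevention in older adults from "disease modification and secondary or tertiary prevention in adults whom AD pathological changes are already in motion".

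**Outcomes.** Section 3.3.1 item 3 lists Aβ42/40, phospho-tau, total tau and/or neurofilament light, and says these "may be compared within subjects over time and between subjects and groups". Item 4 covers stimulation of blood cells with Aβ42, which it describes as having "immunostimulatory / inflammatory effects that increase with AD progression".

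**Samples.** Sections 6.2.2 and 6.3.4 provide a lumbar puncture at Baseline, listed ahead of the first vaccination, and another at Day 84. The supernatant is frozen and assayed later.

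**Analysis.** Section 8.1 describes change and tests it within subjects by paired t-test or Wilcoxon test. It pre-specifies no comparisons and treats every outcome as exploratory. No positivity cut-off and no summary by Baseline amyloid status appears anywhere.

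**The concern.** The primary objective in section 3.2 is to pick the most promising biomarkers, and response to BCG is one of the three things they are judged on. For the Aβ42-stimulated response the protocol itself names AD state as something that changes the outcome. The only subject labels it defines are clinical ones, and by its own account MCI does not guarantee AD pathology. Nothing keeps amyloid-positive subjects out of the normal cohort either.

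If a marker responds to BCG mainly where amyloid is present, the pooled change and the change within each clinical cohort both average that response with subjects who do not show it. A useful marker could then look weak. The study would also hand on little information about which of the programme's two target populations, prevention or disease modification, a marker suits. The material needed to look at this is already being collected.

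**Working it through.** The plan contains no sample size, power or effect figure, so there is nothing of its own to reproduce. The first step is a reading of the text. The later steps illustrate size under stated assumptions.

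**1. Does anything in the text fix amyloid status?** The criteria nearest to the cause of impairment are exclusion 13 ("Other/confounding neurological or psychiatric condition, unstable medical or psychiatric conditions") and exclusion 14 (laboratory findings such as B12, folate and TSH). They remove some other causes but neither require nor exclude amyloid. The text therefore permits both cohorts to be mixed.

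**2. Would they be mixed?** Let p be the amyloid-positive share of a cohort (assumed; the documents give none).
- Chance that 10 MCI subjects include both types, 1 − p¹⁰ − (1 − p)¹⁰: 99.8% at p = 0.5, 97% at 0.7, 89% at 0.8, 65% at 0.9.
- Chance of at least one positive among 10 normal subjects, 1 − (1 − p)¹⁰: 65% at p = 0.1, 89% at 0.2, 97% at 0.3.

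Mixing is likely over a wide range.

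**3. How much could the average hide?** Let δ be the mean change in positives and rδ the mean change in negatives. The averaged change, as a fraction of δ, is p + (1 − p)r. Assume p = 0.40-0.60 in MCI and 0.15-0.30 in normals.
- Share positive among all 20: (10 × 0.40 + 10 × 0.15)/20 = 5.5/20 = 27.5%, up to (10 × 0.60 + 10 × 0.30)/20 = 9/20 = 45%.

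| Response in negatives | MCI cohort | All 20 |
|---|---|---|
| None (r = 0) | 40-60% of δ | 27.5-45% of δ |
| Half (r = 0.5) | 0.40 + 0.60 × 0.5 = 70% to 0.60 + 0.40 × 0.5 = 80% | 0.275 + 0.725 × 0.5 = 64% to 0.45 + 0.55 × 0.5 = 72.5% |
| Same (r = 1) | 100% | 100% |

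The r = 0 row is the extreme case.

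**4. Are the planned tests wrong?** No. Each subject is their own control, so stable differences between subjects cancel. The paired test is a valid test of average change in the sample. What is missing is any view of whether that average conceals two different responses.

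**5. Is grouping by Baseline Aβ42/40 safe for every outcome?** Not for change in Aβ42/40 itself. With no treatment effect, equal variances and correlation ρ between visits, the expected change given Baseline value x is −(1 − ρ)(x − mean). For an assumed ρ of 0.9, a subject drifts back by 10% of the distance from the mean; for 0.8, by 20%. Section 3.3.1 claims good stability for its assays but gives no figure. With no control arm, this drift cannot be separated from a BCG effect. The Aβ42-stimulated response and the other markers are not being grouped on their own Baseline value, so this direct problem does not arise for them.

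**6. How many subjects per group?** Under the same shares, 5.5 to 9 positives are expected among 20. Sections 7.4 and 8.1 give a total of 12; split evenly that means 6 × 0.40 + 6 × 0.15 = 3.3 to 6 × 0.60 + 6 × 0.30 = 5.4 positives.

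**The case against.** **The study is a descriptive pilot.** Outcomes are exploratory, no claims attach to them, and no rule drops a marker for a small pooled response; feasibility and technical performance count as well. Target engagement and the general immune markers are not described as depending on amyloid. This stands, and it limits the weight of the point. It excuses the absence of power and multiplicity control, but it is no reason to leave the groups undefined or to omit an inexpensive display.

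**Clinical groups have their own rationale.** Section 2.1.2 contrasts MCI or AD with healthy controls in monocyte response to amyloid, and says that T-cell reactivity rises with age as well as with AD progression. This stands too: amyloid status should supplement the normal/MCI display, not replace it as the one correct grouping.

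**The size is assumed.** Both the shares and the all-or-none response are assumptions. The protocol speaks of effects that increase with progression, which points to a smaller loss than the r = 0 row.

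**Stronger readings that the documents do not support:**
- A reader might infer that the plan compares AD-marker and Aβ42 responses between mixed cohorts, and that a normal-versus-MCI difference would be credited to AD. Item 3 only allows such a comparison, item 4 states none between cohorts, and section 8.1 names only within-subject tests.
- A reader might infer that Baseline CSF already identifies who is amyloid-positive. It could do so. However, the marker list is joined by and/or, the samples are assayed later, section 6.2.8 foresees failed procedures, and no cut-off is recorded.
- A reader might infer that the MCI cohort has no tie to AD at all. It rests on a named NIA-AA definition, and the documents do not say whether biomarkers were part of applying it.

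**Conclusion.** The point holds as a gap in analysis and interpretation, not as an error in a planned test. The cohorts are clinical, the protocol expects at least one AD outcome to vary with AD progression, and pre-dose CSF is collected, but no summary by Baseline amyloid status is planned. The paired tests stay valid; they can hide a response that differs by amyloid status.

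The size cannot be derived from the documents. It ranges from no loss, if positives and negatives respond alike, to a response seen at 40-60% of its size in the MCI cohort and 27.5-45% in all 20, if only positives respond and the assumed shares (40-60% of MCI, 15-30% of normals) apply. The finding supports a descriptive addition and nothing stronger.

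**What to change.** In section 3.3.1 items 3 and 4, and in section 8.1:

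1. Define the groups.
2. Commit to measuring CSF Aβ42/40 at Baseline in every subject with a CSF sample.
3. State the positivity cut-off before the data are examined.
4. Show change in the Aβ42-stimulated response and in the AD markers descriptively by Baseline amyloid status and against continuous Baseline Aβ42/40, alongside the normal/MCI display.
5. For change in Aβ42/40 itself, note that grouping by its own Baseline value is subject to regression to the mean, and do not read that display as a BCG response.
6. Make no subgroup significance claims.

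Reconcile the total as well: 20 in section 3.1, 12 in sections 7.4 and 8.1.

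The cost is a wording change, one further set of summaries, and a firm commitment to an assay that is already on the list. Eligibility, visits and procedures are unchanged. The drawback is small and uneven subgroups, which is why the display stays descriptive.
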